7.7 Randomisation

Randomisation should not take place until written informed consent (or consultee/Legal Representative approval for those lacking capacity) is obtained (see section 7.5). Allocation to intervention or control will be by concealed online randomisation. Participants will be randomised in a 1:1 ratio, to usual care without incentive spirometry (control) or usual care plus incentive spirometry (intervention) after consent. Randomisation will be undertaken by individuals trained and delegated for randomisation duties; this could be clinicians or research delivery staff. Randomisation will be stratified by site and minimised by consent status (self-consent or consultee/PLR approval) and co-existing injury status (isolated rib fracture(s) or rib fractures and ≥ 1 confirmed acute injury). Randomisation will be by means of a computer-generated code, with allocation concealed from the recruiter by use of a remote (web) randomisation service (Sealed Envelope). In the event of technical failure accessing the online randomisation system, recruiting staff will be encouraged to contact the Bristol Trials Centre (BTC) central coordination team to perform a manual randomisation.

The randomisation procedure will involve a delegated member of the research team signing into the trial database and adding a new participant, which will generate their unique Study ID. They will then enter information to confirm participant eligibility, and complete a form to confirm that valid consent has been received. They will then be required to enter relevant stratification and minimisation variables. Randomisation data will then be sent securely to Sealed Envelope and the allocation of intervention, (incentive spirometry and usual care) or control, (usual care without incentive spirometry), will be immediately returned in the study database. The online randomisation system will automatically send an email to relevant users with ‘notifications enabled’ confirming the randomisation. Appropriate site staff will place a record (electronic or print out) of the allocation generated by the randomisation system in the participant’s medical notes.

Once a participant has been randomised, they are enrolled in the study and treatment can proceed. Hospital (site/equivalent research) staff should proceed to complete and send a study approved letter to the participant’s GP (e.g. via post or secure email), including a copy of their patient’s completed consent form (or declaration form where appropriate), informing the GP that their patient has entered the trial; a copy of this letter should also be filed in the ISF.

Medical case notes containing source data or other trial-related information should also be identified by a label (or equivalent for electronic notes, where feasible), e.g. “Keep until at least dd/mm/yyyy” where the date given is at least five years after the end of the trial.

7.8 Schedule of assessments and data collection

Activity/ Assessment	Enrolment	Randomisation/ Baseline	Initial teaching session †	Additional teaching†*	Follow-up			As required
Time point	Day 0 (-1)	Day 0	Day 0 (+2)	Day 0 (+≤5)	Day 5	Day 5(+2)	Day 30	Up to Day 30
Screening	X							
Consent	X							
Sociodemographic Details		X						
Injury Details		X						
Co-morbidities		X						
Clinical Frailty Scale (Rockwood)		X						
Initial incentive Spirometry Teaching Session †			X					
Up to 2 additional incentive spirometry teaching sessions†				X*				
Adherence					X			
Primary outcome					X			
Secondary outcomes (PROMS)		X				X		
Length of stay (hospital and critical care/ HDU admission)							X	
Details of re-attendances to A&E or unplanned re-admissions							X	
Mortality						X	X	

Safety Reporting CRF								X
Change of Status CRF								X

t Intervention arm only

**only if required*

7.9 Screening and Baseline Data Collection

A screening CRF will be completed for each participant that presents, meeting the inclusion criteria. Data capture on this CRF will include (but is not limited to):

- Age
- Sex
- Preferred language
- Eligibility criteria and confirmation of eligibility status
- Approach details and outcome (e.g. decline reasons)

During online randomisation, data capture will include eligibility criteria, mental capacity status, co-existing injury status (binary). During screening, patients' initials and year of birth will be recorded to ensure correct identification of patients at site.

Patient Reported Outcomes (participants): Site staff should endeavour to conduct patient reported outcome measures (PROMS) at the time of enrolment (consent). However, it is acknowledged that this may not be feasible, or appropriate, if e.g. the patient is fatigued or breathless following the consent discussion. As such, PROMS can be delayed but, like randomisation, should be completed within 24hours of being admitted to hospital. Participants will be asked to complete the PROMs according to how they feel at the time of completion. They may be completed with the assistance of a researcher/member of the clinical team (or person with caring responsibility, e.g. family member, if/where feasible).

CRF (site staff): A delegated site staff member will complete the Baseline CRF. Data capture on this CRF will include (but is not limited to):

- Patient name and contact details
- Patient demographics, including (confirmed) date of birth, ethnicity and gender
- GP (Practice) contact details
- Details of Personal Consultee/PLR (if relevant)
- Admission details
- Injury Details
- History of any chronic lung disease
- Pre-injury anticoagulant use
- Clinical observations
- Rockwood clinical frailty scale

- Intervention fidelity (provision of incentive spirometers to intervention participants only)

7.10 Data Collection at Day 5

Participants who remain in hospital at 5-days post-randomisation (+2 days):

A member of the site research team will ask these participants to complete the 5-day PROMs. These can be entered directly into the database by site staff or completed on paper CRFs downloaded from the study database by site staff for participants.

For patients who have mild/moderate cognitive impairment (e.g. due to Alzheimer's disease), the PROMs may be completed with the assistance of a researcher/member of the clinical team (or person with caring responsibility if/where feasible); if in such participants it becomes unfeasible to complete the PROMS (or elements of it), site staff should record this in the 5-day CRF.

Participants who have transferred to a different hospital or who have been discharged from hospital at 5-days post-randomisation (+2 days):

Follow up will be completed remotely using a range of available methods to suit the participant's preferences and location (e.g. via telephone or site staff at receiving hospital if transferred to another trial site). If the participant does not have capacity, where possible, then a consultee (and/or person with caring responsibility) will be asked to assist the participant to complete the PROMS. If it is not feasible for the participant to complete (part of) the PROMs, site staff should record this in the 5-day CRF.

7.11 Follow up Data Collection at Day 30

CRF (site staff): A delegated site staff member will complete the 30-day CRF. Data capture on this CRF will include (but is not limited to):

- Hospital admission details, including discharge status and date (where applicable)
- Mortality data
- Resource use e.g. admission to critical care (including HDU) during index admission; any unplanned readmissions within 30 days

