6.6.1 General information

Patients randomised to the intervention arm will be issued with an incentive spirometer as soon as is practical and immediate care needs have been addressed. Each participating hospital will procure its own devices to ensure the generalisability of results across diverse clinical settings and to streamline logistical coordination. Restrictions will not be placed on brand or manufacturer but data on the type of incentive spirometer (volume or flow) will be collected.

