7.3 Screening and identification of participants

Hospital staff will be asked to complete a trial-specific screening Case Report Form (CRF) for each patient aged ≥ 65 years admitted to that hospital with acute rib fracture(s) following blunt chest wall trauma.

Recruitment will be undertaken 24 hours a day, 7 days a week. Potentially eligible participants will be identified by clinical staff or research delivery staff (e.g. Research Nurses/Physiotherapists) at the time of arrival in ED or on/after transfer to inpatient settings (e.g. ward, acute medical/surgical assessment unit). Upon identifying a (potentially) eligible patient, a member of the clinical team or research practitioner will give the patient the written study Summary Participant Information Sheet (Summary PIS) and, where appropriate, the full Participant Information Sheet (Detailed PIS) (e.g. the patient has read the Summary PIS and requested further information and/or is suitably comfortable and able to read both documents at that time). We recognise that our target population is older adults. Patient information materials will therefore be available in a variety of formats, including paper (normal and large print) and video, as advised by our patient groups to maximise participation across all potentially eligible patients.

Patients will be given sufficient time to read/view the information material and ask any questions they may have about the trial. The length of time patients will have to consider participation will vary due to the nature of EDs and assessment pathways. If appropriate, consent can be received whilst the patient is still within the ED, however consent will not be taken until immediate care needs have been addressed. When considering participation in the emergency setting, patient consideration-time is estimated to be from one to four hours; this approach is considered acceptable by patients, as demonstrated by other ED-based research undertaken by our group (^{5,26}). If required, the participant can be given longer to consider involvement even if transferred to a ward. However, due to the need for early intervention, a maximum of 24 hours from admission to randomisation will be set (and written consent must be received prior to randomisation).

In patients without capacity, we will seek approval from a patient's personal consultee/legal representative (see section 7.6)

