11 ANALYSES

11.1 Statistical analysis

Analyses will be directed by a pre-specified Statistical Analysis Plan (SAP) and will be in line with CONSORT reporting guidelines for clinical trials. Participant flow will be reported in a CONSORT flow chart (²⁹). Participant baseline characteristics will be reported, overall and by randomised allocation, using descriptive statistics.

Continuous data will be summarised as mean and SD or median and inter-quartile range (IQR) if distributions are skewed. Categorical data will be summarised as number and percentages. The primary analysis will be conducted under the intention-to-treat approach, consisting of logistic regression of presence vs absence of pulmonary complications on allocation, adjusted for site, capacity status, and co-existing injury status (design variables). Results will be reported as an odds ratio with associated 95% confidence interval and p-value. Result will also be presented as an absolute difference and Number Needed to Treat for completeness. Secondary outcome analysis will be consistent with that described for the primary outcome, using a form of regression appropriate to the nature of the outcome being analysed (linear regression for continuous outcome, logistic regression for binary outcome etc), plus additional adjustment for baseline value of outcome where relevant. A repeat analysis of the primary outcome using a Complier Average Causal Effect analysis, with reporting of treatment effect based on adherence, will be considered. Sensitivity of the primary analysis to the impact of missing data will be explored.

Model validity will be checked using standard methods; if a model is a poor fit, alternative models or transformations will be explored.

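### Baseline breathlessness and pain scores may be taken after allocation is known, so adjusting for them can bias two secondary estimates

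*Protocol*

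**What the plan says.** **Default timing.** Section 7.9 asks site staff to try to collect the patient-reported measures at consent, which must come before randomisation. This is an aim, not a requirement.

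**Permitted delay.** Where that is not feasible or appropriate, for example in a patient left tired or short of breath by the consent discussion, "PROMS can be delayed but, like randomisation, should be completed within 24hours of being admitted to hospital". The score reflects the moment it is given: "Participants will be asked to complete the PROMs according to how they feel at the time of completion".

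**Randomisation window.** Section 7.3 uses the same clock: "a maximum of 24 hours from admission to randomisation will be set".

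**What precedes allocation.** Under section 7.7 staff confirm eligibility and consent, and then: "They will then be required to enter relevant stratification and minimisation variables". The allocation "will be immediately returned in the study database". No questionnaire is among the required entries.

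**What follows allocation.** Section 7.7 lets treatment proceed once the participant is randomised. Under section 6.6.1, intervention participants "will be issued with an incentive spirometer as soon as is practical and immediate care needs have been addressed". The schedule in section 7.8 allows the first teaching session from Day 0 to two days later. Section 7.12 states that participants and local teams cannot be blinded.

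**Use in analysis.** Section 11.1 models secondary outcomes in the same way as the primary, "plus additional adjustment for baseline value of outcome where relevant". Breathlessness and pain are the only secondary outcomes in section 6.7.2 with a baseline value.

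**The concern.** A baseline covariate is safe to adjust for because allocation cannot have influenced it. Here the questionnaire window and the randomisation window share one end point, 24 hours from admission, and no order is set between them. If the score is given after allocation, it may already carry an effect of the allocation, through knowing the arm or through early use of the device. Adjusting for it then subtracts part of that effect from the Day 5 comparison, or adds to it.

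The exposure is unlikely to be random across patients. Those whose questionnaires may be put off are the tired and the breathless, and breathlessness is what Dyspnea-12 measures. Section 8.6 also lists a passing increase in shortness of breath as expected with spirometry. That is a route by which early use could raise the so-called baseline in one arm only.

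At stake are the adjusted estimates for two secondary outcomes.

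**Working it through.** **1. Does the text permit it?** Take a participant randomised at hour 3 after admission, taught to use the device soon afterwards, and scored at hour 20 (hours chosen for illustration).
- Randomisation within 24 hours of admission (7.3): met.
- Questionnaires within 24 hours of admission (7.9): met.
- Consent before trial assessments (7.5): met.
- Required entries before allocation is returned (7.7): met without a questionnaire.
- First teaching on Day 0 (7.8): allowed.

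No rule is broken, and the hour-20 score is the recorded baseline. The schedule does not settle the order, because it places the questionnaires in a joint randomisation and baseline column on Day 0. Nor does the label baseline imply pre-allocation: the Baseline CRF also records whether the spirometer was provided (6.6.4, 7.9), which can be known only afterwards.

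**2. Form of the bias.** Let b be the within-arm slope of the Day 5 score on the baseline score, f the share of intervention-arm baselines taken after allocation, and d the shift that allocation or device use causes in those scores relative to control. Then

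expected adjusted difference = true difference − b × f × d.

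Lower scores are better. If early use brings relief (d < 0), the term is positive and a true benefit is attenuated. If it brings discomfort (d > 0), the benefit is exaggerated.

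**3. Size in points.** The protocol gives no value for b, f or d, so all three are assumptions; the pain scale is taken as 0–10.

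| b | f | d (points) | bias, absolute (points) |
|---|---|---|---|
| 0.4 | 10% | 0.5 | 0.4 × 0.10 × 0.5 = 0.02 |
| 0.6 | 50% | 1.0 | 0.6 × 0.50 × 1.0 = 0.30 |

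**4. Size in SD units.** For b = 0.3 to 0.7, f = 10 to 50% and d = 0.1 to 0.3 SD, the absolute bias runs from 0.3 × 0.10 × 0.1 = 0.003 SD to 0.7 × 0.50 × 0.3 = 0.105 SD.

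**5. Simulation.** 248 participants, b = 0.5, true effect −0.30 SD, 4,000 replicates, late scores falling at random:

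| f | d (SD) | mean adjusted estimate (SD) |
|---|---|---|
| 0 | – | −0.30 |
| 25% | −0.3 | −0.26 |
| 50% | −0.3 | −0.23 |
| 50% | +0.3 | −0.37 |

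These agree with the formula: at f = 50% and d = ±0.3 the bias is 0.5 × 0.5 × 0.3 = 0.075 SD. With every score taken before allocation it is zero.

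**6. Sample size.** The protocol states no figure for the patient-reported outcomes. Its sample size concerns the primary outcome and reproduces: 50% versus 30%, two-sided 5%, 90% power gives 124 per arm, 248 in all, and 248 / 0.9 = 275.6, rounded up to 276. Nothing here changes it.

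**The case against.** **Consent-time collection is the default.** This stands. Late scores are an exception, the first teaching session may come as late as Day 2, and the order of columns in the schedule suggests baseline was meant to come first. The share of late scores may be small. But the exception is written into the protocol, and knowledge of allocation alone can alter a self-report before the device is used.

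**A reader might infer that randomisation no longer protects the two comparisons.** The documents do not support that. Day 5 scores are still compared between randomised groups, and an estimate not adjusted for the baseline questionnaire score is free of this problem. Only the adjustment is exposed.

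**A reader might put the pain bias at 0.2 to 0.6 points.** Those figures (0.4 × 0.5 and 0.6 × 1.0) require every intervention-arm score to be late and shifted, which the stated default makes implausible. Even a shift of 0.5 to 1.0 point within a day is an assumption: section 3.1 reports that older patients who tried the device said it did not worsen their pain.

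**The SAP could deal with it.** In part. It could set late scores aside or drop the adjustment, provided completion times are captured. The CRF lists are not exhaustive, so the absence of a time stamp is not shown. But no analysis can recover a pre-allocation score that was never collected.

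**Open-label Day 5 self-reports are exposed to reporting bias anyway.** True, but that is a separate problem, and this one is avoidable.

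**Conclusion.** The gap is real and modest. Section 7.9 permits a delayed score to be given after allocation is known and spirometry has begun, and section 11.1 would treat it as baseline. The adjusted estimates for breathlessness and pain can be biased, in a direction that cannot be fixed in advance. On the assumptions above the bias is about 0.02 to 0.30 points for pain, or 0.003 to 0.105 SD on either measure; it vanishes if no score is late or if allocation does not shift the late ones. The textual finding is firm; the size is illustrative only. It would be wrong to extend the point to the primary outcome, the sample size or the unadjusted Day 5 comparisons. It merits correction because the remedy is cheap and has to be made at data collection.

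**What to change.** - In section 7.9, state that baseline questionnaires are completed after consent and before the randomisation form is submitted. Allow an unable-to-complete entry so that randomisation is never held up.
- Record the completion time, so that it can be compared with the times of randomisation and device issue.
- Treat any score timed after randomisation as a missing baseline, handled by mean imputation or a missing indicator so that no participant is dropped. Whether a score existed at randomisation is settled before allocation, so this handling does not depend on the arm.
- Add a sensitivity analysis for both outcomes without adjustment for the baseline questionnaire score.

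Cost: one sentence in the protocol, a database check and a time field. There will be somewhat more missing baseline scores, mainly in patients too unwell to answer, with a slight loss of precision. It also adds a short step to round-the-clock recruitment, which the unable-to-complete entry keeps small. The targets of 248 and 276 do not change.

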3 TRIAL SUMMARY

Trial Title	Randomised Evaluation of incentive Spirometry in OLder adults with rib fractures to preVEnt pulmonary complications	
Short title	RESOLVE	
Chief Investigator	[name]	
Joint Lead	[name]	
Sponsor	North Bristol NHS Trust (R&D)	
Funder	National Institute for Health and Care Research (NIHR) Research for Patient Benefit (RfPB) Programme	
Trial Design	Prospective multicentre parallel group randomised controlled superiority trial	
Trial Participants	Adults aged ≥ 65 years presenting to UK Emergency Departments with traumatic rib fracture(s)	
Target sample size	276	
Target number of study sites	12	
Intervention	Incentive spirometry (and usual care)	
Treatment duration	Minimum 72 hours	
Inclusion criteria	
 • Aged ≥ 65 years • Radiological evidence of acute rib fracture(s) • Planned for admission • Has capacity to provide informed consent or personal consultee/legal representative available and able to support use of incentive spirometer 	
Exclusion criteria	
 • Co-existing injury or condition for which treating clinician deems patient unable to use incentive spirometer (e.g. facial injuries; burns to both hands; advanced dementia) • Patients who have SpO₂ <92% on air at time of screening (<88% for known chronic lung disease) • Intubated • Haemodynamic instability (e.g severe hypo- or hypertension, significant atrial/ventricular arrhythmia) • History of eye, inner ear or brain surgery within previous four weeks (Contraindication to using incentive spirometry) • 	
	Objectives	Outcome measures
Primary outcome	Onset of new pulmonary complications within 5 days of randomisation	Patient medical notes/EPR (see 6.6.1 for further detail) GP records*

Secondary outcomes	Patient reported breathlessness at 5 days (+2)	The Dyspnea-12 Questionnaire
	Patient reported pain at 5 days (+2)	Numeric Pain Rating Scale
	Length of stay up to 30 days post randomisation	Patient medical notes/EPR
	Admission to Critical Care/ICU up to 30 days post randomisation	Patient medical notes/EPR
	Mortality up to 30 days post randomisation	Patient medical notes/EPR
	Hospital readmission rates up to 30 days post randomisation	Patient medical notes/EPR
Internal pilot	Internal pilot progression criteria will be reviewed after 4 months of active recruitment. See section 6.3 for further detail.	

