5.3 Secondary objectives

To compare the effect on patient reported outcome measures of breathlessness and pain 5 days post randomisation, and the length of initial hospital stay, the rate of admission to critical care, mortality and hospital readmission rates within 30 days of randomisation.

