6.7.2 Secondary outcomes

- Patient reported breathlessness at baseline and 5 (+2*) days (The Dyspnea-12 Questionnaire)
- Patient reported pain at baseline and 5 (+2*) days (Numeric Pain Rating Scale)
- Length of initial stay up to 30 days post randomisation
- Admission to Critical Care up to 30 days post randomisation
- Mortality up to 30 days post randomisation
- Hospital readmission within 30 days of randomisation

*Pain and breathlessness scores will be collected on day 5 where possible but a +2-day window will be accepted to accommodate lack of weekend staffing.

It is anticipated that the majority of patients will remain inpatients on day 5 and patient reported outcome measures can be collected in person by local site staff. For any patients discharged prior to day 5, follow-up can be completed remotely by telephone. The Dyspnea-12 questionnaire and Numeric Pain Rating Scale are both possible to complete by telephone. The researcher will make (up to) three contact attempts. If no response is received, the questionnaires will be marked as missing.

As the Dyspnea-12 Questionnaire includes a question pertaining to depressive symptoms, any participant identified as indicating severe levels of depression will be encouraged by local site staff to seek further evaluation or support from their treating clinician or General Practitioner.

The NPRS has been reported suitable to use with people with mild to moderate cognitive impairment (²⁴). We are unable to find a breathlessness patient reported outcome, suitable for trauma, that has been validated for cognitive impairment in this population. It is recognised that some data for this secondary outcome may be missing for those with mild to moderate cognitive impairment. However, “here and now” symptom self-reporting tools have been shown to be valid and reliable in persons with mild cognitive impairment in previous literature (²⁵) and use of the dyspnea-12 questionnaire in this

trial is supported by our patient and public involvement representatives. Secondary outcomes measured up to 30 days post randomisation will be collected by research staff from their hospital's electronic patient record.

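### Critical-care admission is defined from randomisation to day 30 but collected over the index admission, so placements before allocation can be counted as events

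*Protocol*

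**What the plan says.** **Definition.** Section 6.7.2 lists "Admission to Critical Care up to 30 days post randomisation". The trial summary (section 3) has "Admission to Critical Care/ICU up to 30 days post randomisation". Section 5.3 sets the objective as comparing "the rate of admission to critical care, mortality and hospital readmission rates within 30 days of randomisation". All three tie the outcome to randomisation, and none mentions HDU.

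**Collection.** Section 7.11, under resource use on the 30-day CRF, names "admission to critical care (including HDU) during index admission". The schedule in section 7.8 has a day-30 row for "Length of stay (hospital and critical care/ HDU admission"). Both include HDU, and neither starts the clock at randomisation.

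**Time before allocation.** Section 7.3 states that "a maximum of 24 hours from admission to randomisation will be set". It allows patients to be identified "at the time of arrival in ED or on/after transfer to inpatient settings", with a ward or an assessment unit given as examples.

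**Eligibility.** Section 6.5.1 excludes patients who are intubated, haemodynamically unstable or below the SpO₂ limits on air. Being in HDU or critical care is not itself an exclusion.

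**Contrast.** Section 6.7.1 has an explicit rule that pulmonary complications already evident before randomisation do not meet the primary outcome. Critical-care admission has no equivalent.

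**The concern.** The outcome runs on one clock and its named data item on another. Consider a participant who goes from ED to HDU at 14:00, is randomised at 20:00, steps down the next day and needs no further critical care. The section 6.7.2 definition makes this a non-event. The section 7.11 item, read on its own, is positive. A second participant, in HDU at randomisation and later moved to ICU with pneumonia, is also positive on that item. Only the second case could reflect the allocated treatment.

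If the item feeds the analysis without dates, placements that allocation cannot have caused enter both arms in equal expected proportion. The reported rate then mixes the admission pathway with later deterioration, and the estimated effect is diluted. An analysis plan written later cannot recover timing that was never collected.

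**Working it through.** **1. The plan's own figure.** The only sample size is for the primary outcome (section 6.7.4): 50% v 30%, 90% power, 5% alpha (two-sided assumed). Using the pooled-variance normal approximation,

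n = [1.96·√(2·0.4·0.6) + 1.2816·√(0.5·0.5 + 0.3·0.7)]² / 0.20² = 124 per arm, or 248 in total; 248 / 0.9 = 275.6, rounded up to 276.

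Both stated figures reproduce, and neither depends on the critical-care outcome.

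**2. Windows side by side.**

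| | Start | End | Units named |
|---|---|---|---|
| Outcome, 6.7.2 | randomisation | day 30 | Critical Care |
| Outcome, section 3 | randomisation | day 30 | Critical Care/ICU |
| Data item, 7.11 | index admission, up to 24 h before randomisation | end of index admission, or CRF completion if earlier | critical care including HDU |

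The start differs, and so do the units. Including HDU makes a placement before randomisation more plausible.

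**3. Size if earlier placements were counted.** Let q be the share already in critical care or HDU at randomisation, equal in expectation between arms. Let p be the rate of new admission afterwards in the rest. Then

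observed rate = q + (1 − q)·p.

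The absolute difference shrinks by the factor (1 − q). The protocol gives neither q nor p, so all the values below are assumptions.

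Worked case, p = 10% v 5%:
- q = 0: odds ratio = (0.05/0.95) / (0.10/0.90) = 0.47.
- q = 10%: control 0.10 + 0.90·0.10 = 0.190; intervention 0.10 + 0.90·0.05 = 0.145. Odds ratio = (0.145/0.855) / (0.190/0.810) = 0.72. The difference falls from 5.0 to 4.5 percentage points.

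Range, with 276/2 = 138 per arm and two-sided 5%:

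| New admissions (control v intervention) | q | Odds ratio if earlier placements count | Power |
|---|---|---|---|
| 10% v 5% | 0 | 0.47 | 35% |
| | 5% | 0.64 | 23% |
| | 10% | 0.72 | 17% |
| | 20% | 0.81 | 11% |
| 20% v 10% | 0 | 0.44 | 64% |
| | 5% | 0.54 | 52% |
| | 10% | 0.60 | 42% |
| | 20% | 0.69 | 30% |

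**4. What counting only new episodes recovers.** Keep everyone in the analysis and suppose, for simplicity, that those already there have no new episode. At 10% v 5% and q = 10% the rates are 0.90·0.10 = 9.0% v 0.90·0.05 = 4.5%. The odds ratio is (0.045/0.955) / (0.090/0.910) = 0.48 and power is 32%. Most of the loss is avoided, but the 35% seen at q = 0 is not fully restored.

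**The case against.** A reader might infer that the protocol scores placements before allocation as outcome events. It does not say so. The outcome is tied to randomisation in three places, and on that definition an earlier placement does not count. The section 7.11 line is an example under resource use, in a list described as not exhaustive, and section 11.4 gives resource-use data a purpose of their own. The CRF is not shown, so a bare yes/no field would be an assumption. A critical-care length of stay normally needs dates, and the baseline CRF (section 7.9) holds admission details that might include location. Section 11.1 allows adjustment for a baseline value where relevant. The three exclusions remove many likely occupants of critical care, and the section 7.3 examples are wards and assessment units. The trial is not powered for this outcome: at 10% v 5%, power is 35% with no dilution at all.

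Much of this stands. It rules out the claim that events are mis-scored, and it means the affected share may be small. It does not remove the mismatch. Length of stay is a duration, and no section names a critical-care start time or location at randomisation. Baseline adjustment would need that location. The exclusions do not bar a stable, self-ventilating HDU patient. A rule for status before randomisation was written for the primary outcome and not for this one.

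**Conclusion.** The point holds as an inconsistency between definition and data collection. The item as worded cannot separate placements before allocation from those after it, and no rule says how to score a participant already in HDU or critical care at randomisation. Such placements can therefore be counted as events unless dates are captured; the documents do not show that they will be.

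If they were counted, the bias would be towards no effect. In the assumed 10% v 5% case, the odds ratio would move from 0.47 to between 0.64 and 0.81 for a share of 5% to 20%. These figures rest on assumed admission rates, an assumed share already in critical care that is equal between arms, and every such patient being scored as an event. The true size cannot be determined from the protocol. One secondary outcome is affected; the primary analysis and the sample size are not. The change is worth making because it is cheap now, and timing is harder to retrieve later.

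**What to change.** - **Definition (sections 3, 5.3, 6.7.2).** Count a new critical-care admission, or a step-up in level of care, that starts after randomisation and no later than day 30. State whether HDU counts, and use the same term throughout, including section 7.8.
- **Data item (section 7.11).** Replace the index-admission window with critical-care episodes starting after randomisation and up to day 30. This also covers critical care during a readmission within 30 days, which the present wording does not reach.
- **Fields.** Record location at randomisation (ED or ward, HDU, ICU) on the baseline CRF, and the start date-time of each critical-care episode on the day-30 CRF.
- **Scoring rule.** A participant already in HDU or critical care at randomisation is an event only for a new episode or step-up afterwards.
- **Optional.** Adjust this outcome for location at randomisation.

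The cost is two short fields from records that site staff already review, plus a few amended lines of protocol. The downside is fewer counted events. In the illustration with q = 10%, and no new episodes among those already there, expected control-arm events fall from 0.190·138 ≈ 26 to 0.090·138 ≈ 12. The events removed are ones that allocation could not have caused.
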